## 7.3 Handling of Missing, Incomplete and Repeat Data

No imputation methods are planned for missing data in this study. Only observed data will be summarized and analyzed.

#### 7.4 Derived Data and Some Other Specific Data to be Summarized

##### Study Windows

6 Month window = 182 Days +/- 91 days

1 Year window = 365 Days +/- 91 days

##### Body Mass Index (BMI)

- $BMI = \text{weight [kg]} / (\text{height [cm]} / 100)^2$

##### Change from baseline

- Change in score between baseline and follow up visits for the relevant assessments will be considered as the difference between the follow up visit and the baseline score (i.e. follow up score – baseline score) except if specifically defined otherwise.

##### Instructions for the creation of the following tables:

- Reason for Revision, Reason for Revision will be derived from the Study Device Revision CRF.
- Study Device Revision, if multiple Reasons for Revision then include and separate with a comma.

#### 7.4.1 Derived Data for the Primary Endpoint

The final count of re-interventions for the 6 month post-operative time point will be defined as any revision that occurred before the end of the 6 Month window (273 days),

i.e. if (Date of Revision – Date of Surgery) < 273 days,

where the Date of Revision is obtained from the Implant Revision CRF and the Surgery Date is obtained from the Operative Data CRF.

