9.3 EXCLUSION CRITERIA

Any one (1) of the following criteria will disqualify a potential subject from participation in the study:

1. Subject is ≤ 6 months post-operative
2. Subject is entered in another investigational drug, biologic, or device study or has been treated with an investigational product within 12 months post-operative.

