12.3 EFFICACY ANALYSIS

12.3.1 Analysis of Primary Endpoint(s)

CONFIDENTIAL AND PROPRIETARY

This document contains information that is confidential and proprietary to Smith & Nephew PLC and Smith & Nephew, Inc. and is intended for use only by Smith & Nephew and its manufacturer. It shall not be reproduced or copied in whole or in part, nor shall the contents be disclosed by any means without prior written permission from Smith & Nephew, nor shall anyone make any use of it that is contrary to the expressed or implied wishes of Smith & Nephew.

Study Protocol—Device	
Safety and Performance of Q-Fix™ All-Suture Anchor System	Number: 17-5010-11
	Version: 2.0 05SEP2019
	Page: Page 30 of 62

Clinical success rate, defined as subjects without re-intervention at 6 months post-operative, as assessed by the surgeon:

The frequency of the subjects without re-intervention at 6 months together with percentage with a 95% CI will be reported. Clinical success rate for the entire sample, as well as by the position (i.e. the hip, shoulder and knee will be reported). This analysis will be carried out using the per protocol population as the primary analysis population with the safety population used for sensitivity analysis.

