#### 5. Study Endpoints

##### 5.1 Primary Endpoints

- Clinical success rate, defined as subjects without re-intervention at 6 months post- operative, as assessed by the surgeon

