#### 7.4.2 Derived Data for the Secondary Endpoints

The final count of re-interventions for the 12 month post-operative time point will be defined as any revision that occurred between the end of the 6 Month window (273 days) and the end of the 12 Month window (456 days) i.e. if (273 days <= Date of Revision – Date of Surgery <= 456 days).

Where the Date of Revision is obtained from the Implant Revision CRF and the Surgery Date is obtained from the Operative Data CRF.

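### The 6-month primary endpoint counts revisions up to day 272 (about 8.9 months), 90 days past the time point it is named for and about 89 days past the elapsed time that eligibility guarantees

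*SAP*

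**What the plan says.** SAP 5.1 gives the primary endpoint as "Clinical success rate, defined as subjects without re-intervention at 6 months post- operative, as assessed by the surgeon". Protocol 12.3.1 carries the same time point into the analysis: "The frequency of the subjects without re-intervention at 6 months together with percentage with a 95% CI will be reported".

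SAP 7.4 sets the visit window: "6 Month window = 182 Days +/- 91 days". SAP 7.4.1 then takes the upper edge of that window as the event cut-off. It counts "any revision that occurred before the end of the 6 Month window (273 days"), coded as "i.e. if (Date of Revision – Date of Surgery) < 273 days", with both dates read from CRFs. SAP 7.4.2 starts the 12-month count where this one stops: "273 days <= Date of Revision – Date of Surgery <= 456 days".

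The only eligibility rule on time since surgery is the exclusion in Protocol 9.3: "Subject is ≤ 6 months post-operative". SAP 7.9.1 analyses the endpoint as a simple proportion with an exact 95% confidence interval, and SAP 7.3 plans no imputation. SAP 7.11 records no change from the protocol's analysis methods, although Protocol 12.3.1 contains no 273-day rule.

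**The concern.** A visit window deals with measurements that are taken when the patient happens to attend. A revision has its own date, and SAP 7.4.1 already subtracts the surgery date from it, so the count could stop at the nominal time point. Stopping at the end of the window instead gives a quantity close to a 9-month rate, still reported under a 6-month name.

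The cut-off also parts company with eligibility. Every eligible subject is more than 6 months from surgery, so day 182 has passed for all of them. Day 273 need not have passed. At stake is whether the headline number of this post-market study estimates what its name says, and whether every subject had the chance to be observed over the whole counting period.

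**Working it through.** **Inputs.** Nominal 6-month day 182, window ±91 days, nominal 12-month day 365 (SAP 7.4). Strict cut-off at 273 days (SAP 7.4.1). Exclusion of subjects 6 months or less from surgery (Protocol 9.3), taken as a minimum of about 183 days elapsed. Follow-up phase of 2 months (Protocol synopsis, Study Duration). One month = 30.4375 days.

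**The plan's own figure.** 182 + 91 = 273, which reproduces the SAP's cut-off. It is not an arithmetic slip. With a strict inequality the last counted day is 272.

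**Length of the counting period.**
- 272 / 30.4375 = 8.94 months, against 182 / 30.4375 = 5.98 months.
- 272 − 182 = 90 extra days, and 90 / 182 = 49% longer.

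**Against eligibility.**
- 272 − 183 = 89 days not guaranteed, and 89 / 272 = 33% of the counting period.
- Crediting the whole 2-month follow-up phase to a subject gives 8 × 30.4375 = 243.5 days, still about 28 days short of day 272.

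**Effect of the longer period, with complete observation.** The documents give no failure-time distribution, so a constant hazard is assumed.
- 5% failing by day 273: h = −ln(0.95) / 273 = 0.000188 per day. Day-182 failure = 1 − exp(−182h) = 3.4%. About one third of the counted failures then fall after day 182. That share is largely a consequence of the constant-hazard assumption (91 / 273 = 33%).
- The other way round, with h = −ln(1 − p) / 182 and day-272 risk = 1 − exp(−272h):

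| Assumed day-182 failure p | Day-272 failure |
|---|---|
| 1.6% | 2.4% |
| 1.8% | 2.7% |
| 5% | 7.4% |

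**Effect of incomplete observation.** Suppose, as an assumption only, that chart review falls uniformly between day 183 and day E, and that a subject reviewed before day 273 with no revision so far is counted as a success. The share not yet at day 273 is 90 / (E − 183). The expected count is the mean of 1 − exp(−h × min(t, 272)), with h as above.

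| Review runs to day E | Share below day 273 | Failure counted |
|---|---|---|
| 365 | 90 / 182 = 49% | 4.6% |
| 456 | 90 / 273 = 33% | 4.7% |
| 730 | 90 / 547 = 16% | 4.9% |

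The comparison values are 3.4% at day 182 and 5.0% at day 273.

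**The 12-month rule.** SAP 7.4.2 counts only days 273 to 456 (365 + 91 = 456). A revision on any day from 0 to 272 is not in the 12-month count, although that subject is not free of re-intervention at 12 months.

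**The case against.** **The window covers more than VAS and ROM.** The schedules in the protocol and the SAP put Implant Status in the same 182 ± 91-day column, and success is to be judged by the surgeon, so closing the count at window end follows the plan's own schedule. This stands as an explanation of where 273 came from. A reader might infer that the window was meant only for VAS and ROM, and the documents do not say that. But a dated event does not need the window, and the endpoint definition still says 6 months.

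**The rule cannot flatter the 6-month result.** This stands. Compared with a day-182 count on the same charts, the SAP rule can only add failures. A reader might infer that 6-month success is overstated. The cut-off does not do that.

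**Eligibility guarantees elapsed time, not charted observation.** This also stands. Data are taken as far as the chart holds them (Protocol 11.1.2), and a patient last seen at week 6 is unobserved at day 182 as well as at day 272. A day-182 cut-off reduces the problem without removing it, and any 12-month rule exceeds the guaranteed elapsed time by more.

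**Short observation counted as success is an inference.** No passage says it outright. SAP 7.2 removes subjects lost to follow-up from the per-protocol set, which is the primary analysis set. SAP 7.3 analyses observed data only, and SAP 7.6 tabulates separately the subjects whose visit window is still open. None of these sets a minimum number of observed days for a success, and Protocol 9.7 ties loss to follow-up to local standard of care. So the possibility remains open, but it is not an established feature of the plan.

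**Many subjects may be well past day 273.** Screening starts with surgeries in the 12 months before IRB approval or from another agreed date, enrollment lasts 16 months, and Protocol 9.8.1 asks for 12-month data on all subjects. The 49% figure assumes that no review takes place after day 365, so it should not be read as an estimate.

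**The practical effect is small.** The study is descriptive, with no performance goal. On 84 evaluable subjects, 4.6% against 3.4% is about 3.9 against 2.8 failures, roughly one subject, beside a stated precision of within 11%. That limits the weight of the point but does not correct the label.

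**Conclusion.** The point holds as a mismatch between the endpoint's definition and its derivation. The failure count called 6-month runs to day 272, which is 90 days (49%) past day 182 and about 89 days past the elapsed time that eligibility guarantees. Even with complete follow-up, the reported figure is close to a 9-month rate.

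Against a true 6-month rate, the direction is known: failures can only be added. The size depends on the assumed constant hazard. With 5% failing by day 273, the day-182 figure is 3.4%.

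The bias from incomplete observation is unknown, because the documents do not say how many subjects are observed to day 273. The illustrative range of 4.6% to 4.9% against 5.0% rests on uniform review times and on short observation counting as success. A reader might conclude that about half the subjects fall short of day 273, or that the reported number is a demonstrated mixture of follow-up times. The documents support neither.

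The sample size does not depend on this cut-off. The change is worth making before database lock, because the dates needed for the event cut-off are already in the plan.

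**What to change.** **SAP 7.4.1.** Define primary failure as Date of Revision minus Date of Surgery ≤ 182 days. Report the day-273 count as a sensitivity analysis.

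**SAP 7.4.2.** Count 12-month failures cumulatively from surgery to day 365, so that earlier failures are no longer left out.

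**SAP 7.4, windows.** Keep ±91 days for assigning visit-based VAS and ROM data.

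**Observation needed for a success, at both time points.** Either count as a success only a subject with chart contact on or after the cut-off day, or use a Kaplan-Meier estimate at that day with censoring at last chart contact. The first option keeps the simple proportion and exact interval of SAP 7.9.1. However, it retains every recorded failure while dropping unobserved non-failures, so it leans towards a higher failure rate. The second option avoids that if censoring is unrelated to failure, but needs a different interval method.

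**Cost.** One line in each of 7.4.1 and 7.4.2, plus a sentence on the observation rule and a check that the date of last chart contact can be obtained from the CRFs. Revisions on days 183 to 272 leave the primary count and appear in the 12-month count. The sensitivity analysis keeps the day-273 result visible.

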#### 7.4.2 Derived Data for the Secondary Endpoints

The final count of re-interventions for the 12 month post-operative time point will be defined as any revision that occurred between the end of the 6 Month window (273 days) and the end of the 12 Month window (456 days) i.e. if (273 days <= Date of Revision – Date of Surgery <= 456 days).

Where the Date of Revision is obtained from the Implant Revision CRF and the Surgery Date is obtained from the Operative Data CRF.

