10.2.2 Secondary Endpoints

- Clinical success rate, defined as subjects without re-intervention at 12 months post- operative, as assessed by the surgeon
- VAS -pain
- ROM
- Clinical success rate in adolescents and young adults, defined as subjects ages 13-21 years of age without re-intervention at 6 and 12 months post-operative

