## Schedule of Assessments

**Table 1. Study Procedures by Visit**

Schedule of events	Chart Review 		
	Screening	182 days post-op (±91 Days)	365 days post-op (± 91 Days )
Inclusion/Exclusion	X		
Case History Review ***	X		
Implant Status 	X	X	X
VAS	X	X	X
ROM	X	X	X
Concomitant Medications, Procedures 	*	*	*
AE Assessment	*	*	*
Serious Adverse Event (SAE) / Adverse Device Effect (ADE) / Device Deficiency (DevD)	*	*	*
End of Study/Subject disposition	*	*	*

Given the retrospective study design, data will be collected to the extent it is available.

Informed consent/waiver of informed consent from the IRB/EC must be obtained prior to retrospective data collection.

Subjects who have undergone a revision procedure of the anchor will be considered terminated from the study from the date of the revision. Study related data will not be collected following the date of the revision.

 Any concomitant medications/ procedures associated with an AE, SAE or SADE will be recorded.

\*if applicable

\*\*\* Review of subject demographics, medical history, operative, post-op, discharge, and cumulative AE's occurring since date of surgery

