## 7.6 Disposition of Subjects

Patient accounting will be presented as follows:

- Complete Data Per Protocol: Subjects with complete data for the primary endpoint, evaluated per protocol, in the window time frame.
- Any Data: Subjects with any follow-up data reviewed or evaluated by investigator (“all evaluated” accounting).
- Theoretically Due: Number of subjects that would have reached the beginning of the study window associated with each visit if all subjects returned.
- Not Yet Overdue: Subjects who have not yet returned visited but whose visiting window is still open.
- Deaths: Cumulative number of subjects that died during or prior to the study visit.
- Revision: Cumulative number of subjects that failed (revision) during or prior to the study visit.
- Expected Visit: Theoretical subjects minus the number of deaths and revisions.
- % Follow-up: Any Data/Expected\*100
- % Follow-up Per Protocol: Complete Data Per Protocol / Expected \*100

Additionally information on subjects discontinued from the study prematurely will be presented, with a breakdown of the reasons for discontinuation as reported in the CRF. The disposition table will be based on the population from the Safety Population. A Disposition table will also be created in order to summarize the outcomes in terms of implants.

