### 7.9.2 Analysis of Secondary Endpoints

- Clinical success rate at 12 months will be analyzed using the same type of analysis carried out on the primary endpoint.
- Clinical success rate at 6 months and at 12 months for subjects 13 to 21 years of age will be analyzed using the same type of analysis carried out on the primary endpoint.
- Device-related re-intervention. All the above variables will be categorical in nature hence frequencies together with percentages will be tabulated for the entire sample as well as by the indication. Available data will be summarized and summary statistics tabulated. For both the ROM and VAS secondary endpoints a 95% Confidence Interval (CI) for the percentage of subjects with clinical success at 6 months and 1 year will be computed using exact methods

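### SAP 7.4.2 leaves every revision before day 273 out of the 12-month failure count, so each one overstates the 12-month success rate

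*SAP*

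**What the plan says.** Protocol 10.2.2 and SAP 5.2 give the 12-month success rate as "defined as subjects without re-intervention at 12 months" after surgery. SAP 7.9.2 adds: "Clinical success rate at 12 months will be analyzed using the same type of analysis carried out on the primary endpoint".

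The counts behind the rates are set in SAP 7.4:

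- **6 months (7.4.1):** "any revision that occurred before the end of the 6 Month window (273 days"), with the formula revision date minus surgery date < 273 days. There is no lower bound.
- **12 months (7.4.2):** "any revision that occurred between the end of the 6 Month window (273 days) and the end of the 12 Month window (456 days"), with the formula 273 ≤ revision date minus surgery date ≤ 456 days.

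SAP 7.4.2 calls this the final count for the 12-month time point. Other sections bear on the denominator:

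- **SAP Table 1, footnote 3:** "Subjects who have undergone a revision procedure of the anchor will be considered terminated from the study from the date of the revision".
- **SAP 7.6:** the disposition table tallies revisions as "Cumulative number of subjects that failed (revision) during or prior to the study visit" and takes expected visits as "Theoretical subjects minus the number of deaths and revisions".
- **SAP 7.3:** "Only observed data will be summarized and analyzed".
- **SAP 7.2:** primary and secondary endpoints use the per-protocol population. The removal reasons it names are loss to follow-up and death, and the list is left open.

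SAP 7.11 declares no change from the protocol's methods.

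**The concern.** A subject revised on day 100 is not free of re-intervention at 12 months, yet the 7.4.2 rule does not count that subject as a 12-month failure. The lower bound of day 273 appears in both the words and the formula, so a programmer who follows the SAP will apply it.

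The 12-month rate is the figure that answers the one-year aim in SAP section 3. The same count feeds the 12-month rates by joint, in ages 13–21 and by anchor size. The error can only favour the device, and a single-arm series has no comparator to offset it. Early revisions can be in the data, because Protocol 9.4 keeps subjects eligible when a re-intervention is found at screening.

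**Working it through.** **The plan's own figures.** SAP 7.4 gives windows of 182 ± 91 and 365 ± 91 days. They end at 182 + 91 = 273 and 365 + 91 = 456, which matches 7.4.1 and 7.4.2.

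**Inputs.** The evaluable n is 84, 28 per joint (SAP 6.1). Planned success is 95% (SAP 6.1), for which the nearest whole count is 4 failures in 84 (4.8%). The split of failures before and after day 273 is not in the documents, so every split is shown.

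**Formulas.** Let a = subjects revised before day 273, b = subjects revised on days 273–456, and n = subjects, taken as one cohort at both times.

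- Endpoint as defined: (n − a − b)/n
- SAP 7.4.2, early-revised subjects kept: (n − b)/n, an overstatement of a/n
- SAP 7.4.2, early-revised subjects dropped: (n − a − b)/(n − a), an overstatement of a(n − a − b)/[n(n − a)]
- 6-month rate: (n − a)/n

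**Results for n = 84 and a + b = 4.** The correct 12-month rate is 80/84 = 95.2% in every row (exact 95% CI 88.3 to 98.7).

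| a | b | As written, kept | As written, dropped | Overstatement in points (kept / dropped) | 6-month rate |
|---|---|---|---|---|---|
| 0 | 4 | 80/84 = 95.2% | 80/84 = 95.2% | 0 / 0 | 100% |
| 1 | 3 | 81/84 = 96.4% | 80/83 = 96.4% | 1.19 / 1.15 | 98.8% |
| 2 | 2 | 82/84 = 97.6% | 80/82 = 97.6% | 2.38 / 2.32 | 97.6% |
| 3 | 1 | 83/84 = 98.8% | 80/81 = 98.8% | 3.57 / 3.53 | 96.4% |
| 4 | 0 | 84/84 = 100% | 80/80 = 100% | 4.76 / 4.76 | 95.2% |

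In the last row with subjects kept, the exact interval is 95.7 to 100, which excludes the correct 95.2%.

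**Order of the two rates.** The 12-month rate exceeds the 6-month rate when b < a (kept) or b < a(n − a)/n (dropped). The rows with a = 3 and a = 4 show this. On one cohort, a cumulative endpoint cannot behave that way.

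**Other sample sizes.** With subjects kept, each early revision adds 1/n:

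- one joint at 28: 3.57 points
- overall at 84: 1.19 points
- overall at 229, the enrolment reported in Protocol 23.3 (106 + 99 + 24): 0.44 points
- overall at the maximum of 450: 0.22 points

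A larger sample does not remove the bias at a given failure rate. With n = 450 and an assumed 23 failures, 12 of them early, the correct rate is 427/450 = 94.9%. The rule as written gives 439/450 = 97.6%, an overstatement of 2.67 points.

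**The case against.** The strongest defence is that 7.4.1 and 7.4.2 define two non-overlapping bins, and that an analyst guided by the endpoint definition in SAP 5.2 would add them. That may have been the intent. But 7.4.2 calls its figure the final count for the 12-month time point, and no section gives a rule for summing. SAP section 2 mentions accompanying table shells. They are not among the documents, so they cannot be relied on to supply one.

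Several narrower points stand:

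- **Denominator.** SAP 7.2 does not name revision as a reason to leave the per-protocol population, and 7.6 is a visit-accounting table. Keeping early-revised subjects is therefore the likelier reading, with an overstatement of a/n. This narrows the finding without removing the bias.
- **Partial safeguard.** Table 7.6 will report cumulative revisions, so an attentive reader could largely recover the right figure.
- **One cohort.** The claim that the 12-month rate cannot exceed the 6-month rate needs the same subjects at both times. Under observed-data rules with differing denominators, even a correct rate could rise.
- **Sample size.** 84 is the planning minimum. At the enrolment already reached, one revision moves the overall rate by less than half a point.
- **Weight.** This is a secondary endpoint in a descriptive study with no success threshold.

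**Conclusion.** The concern holds. As written, SAP 7.4.2 does not measure the stated 12-month endpoint, and it overstates success under either denominator whenever a subject is revised before day 273.

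At n = 84 with 4 assumed failures, the overstatement is 0 to 4.8 points, and it is zero only if no revision is early. If total failures were as low as the 1.6% (Protocol 13, SAP 6.1) or 1.8% (Protocol synopsis) cited from the hip labral-repair study, it would be at most 1.6 to 1.8 points. That study's title concerns intraoperative pullout, so its rate is not a firm limit on re-intervention by 12 months.

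The direction of the error is certain once any early revision exists. Its size rests on the unknown split and, slightly, on the denominator. The 6-month primary endpoint is not affected.

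**What to change.** In SAP 7.4.2, define a 12-month failure as any revision with 0 ≤ revision date minus surgery date ≤ 456 days. State that subjects revised before day 273 stay in the 12-month denominator as failures. Apply the same rule to the 12-month rates by joint, in ages 13–21 and by anchor size.

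Add a sentence on the rest of the denominator. It should say how unrevised subjects are handled when their records end before the 12-month window, since Protocol 9.3 requires only more than 6 months since surgery. A supportive Kaplan-Meier estimate that censors these subjects would be useful but is not needed for the correction. If the day 273–456 count is wanted, report it separately and label it an interval rate.

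The cost is a short SAP amendment before database lock and a small programming change. Both dates are already on the CRFs. The 12-month rate will look less favourable if any revision was early.
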